2.4.5.1 Analyses of the Bone Mineral Density

Analysis of percent change from Baseline in BMD (lumbar spine, total hip, femoral neck) to Week 26, Week 52, and Week 104 will be performed on the safety population, using BMD measurements obtained during the study, regardless of IMP discontinuation and/or introduction of rescue therapy. No statistical significance tests will be performed.

All planned analyses will be performed at each location (lumbar spine, total hip, and femoral neck) separately.

Analysis of the key secondary safety endpoints of percent change from Baseline to Week 26, Week 52, and Week 104 respectively in BMD will be performed by an ANCOVA model using BMD values measured at Baseline and the corresponding time point (observed or imputed). The missing data at endpoint will be imputed by multiple imputation (MI) methods as detailed below.

Missing endpoint data at Week 26, Week 52, or Week 104 will be imputed using a model built separately in each treatment group and estimated from the patients in the same treatment group who prematurely discontinue the IMP before the endpoint (Week 26, Week 52, or Week 104) but have the measurement for the endpoint (retrieved dropouts). The imputation model will include the randomization strata and the baseline value. In cases of non-convergence during the imputations, the offending stratum will be identified and then will be dropped from the model. Considering that the number of retrieved dropout patients in each treatment group is expected to be small, a simple imputation model based on regression will be used with baseline measurement included as the predictor. This will serve as the primary method of imputation for missing data should sampling criteria be satisfied (ie, ≥ 5 retrieved dropouts in each treatment group).

In addition, a sensitivity analysis using a pattern-based multiple imputation method will be performed. The imputation method will be implemented in 3 steps:

1. For missing data at Baseline, a monotone missingness method implemented in PROC MI with monotone regression option will be used to impute the missing data at Baseline. The imputation model will include the randomization strata and BMD measurements at Baseline.
2. In cases that a non-monotone missing data pattern occurs at the intermediate visits, these data points will be imputed using the Markov Chain Monte Carlo (MCMC) option in PROC MI to partially impute missing data at the intermediate visits in order to achieve a monotone missing pattern for all patients. The imputation model will include treatment, BMD measurements at Baseline, Week 26, Week 52, and Week 104.
3. Using the partially and monotone data sets from the MCMC of step 2, the rest of the missing data will be imputed using a sequential imputation approach. Given that the data sets have monotone missing data pattern, the approach will be to consider imputation on a visit (timepoint) by visit (timepoint) basis and conditioning on all visits (timepoints) data. The process will be to repeat, sequentially, in the order specified in the regression model, the imputation of missing values at each visit (timepoint). The imputation model will include treatment, measurements at Baseline, Week 26, Week 52, and Week 104 in the VAR statement.

A top line analysis to evaluate the efficacy will be conducted when all patients have either completed Week 26 or discontinued prior to Week 26.

The imputation model at Week 26 for the topline analysis will include treatment and measurement at Baseline, after missing baseline data imputation as described in step 1 above.

The imputation method will generate multiple complete data sets. The change from Baseline to Week 26, Week 52, and Week 104 will be derived from observed and imputed BMD values.

The derived change from Baseline to each timepoint in each of the complete datasets will be analyzed by the ANCOVA model with treatment groups (sotagliflozin 400 mg, sotagliflozin 200 mg, placebo), randomization stratum of HbA1c ($\leq 8.5\%$, $> 8.5\%$), randomization stratum of sex (male, female), country as fixed effects, and baseline BMD value as a covariate.

Results from each complete data set will be combined using Rubin's rule to provide the adjusted mean change in BMD from Baseline to each timepoint (Week 26, Week 52, and Week 104) for each treatment group, as well as the between-group difference (comparing sotagliflozin 400 mg or sotagliflozin 200mg vs placebo) and the 95% confidence interval (CI).

This sensitivity analysis will serve as the primary analysis at any timepoint if the number of patients who prematurely discontinue the IMP before the post-Baseline visit (Week 26, Week 52, or Week 104) with the visit data is not sufficient to perform a retrieved dropout analysis.

Descriptive analyses will be performed on the key safety endpoints to summarize the treatment effects across subgroups defined by the following baseline or screening factors:

- Age group (< 65 years, ≥ 65 years).
- Duration of T2D (< 10 years, ≥ 10 years).
- Sex (male, female).
- Baseline BMI level (< 25 ; 25 to < 35 ; ≥ 35 kg/m²).
- Baseline eGFR (< 45 ; 45 to < 60 ; ≥ 60 mL/min/1.73 m²).

The treatment effects (sotagliflozin 400 mg and sotagliflozin 200 mg versus placebo respectively) across the subgroups defined for each of these factors will be estimated for the percent change from Baseline to Week 26, Week 52, and Week 104 in BMD in the safety population, and using the same MI method as applied to each of the key safety endpoints, respectively.

The ANCOVA model will include treatment groups (sotagliflozin 400 mg, sotagliflozin 200 mg, placebo), randomization stratum of HbA1c ($\leq 8.5\%$, $> 8.5\%$), randomization stratum of sex (male, female), subgroup factor, treatment-by-subgroup factor, and country as fixed effects, and baseline BMD value as covariate.

The adjusted estimates of treatment mean differences with SE and 95% CIs will be provided as appropriate across the subgroups (comparing each sotagliflozin group vs placebo group) with SE and 95% CIs will be provided as appropriate across the subgroups. A forest plot of the results will also be presented.

In the case that the subgroup factor is the sex only the subgroup factor (as a single factor and/or an interaction term) will be included in the model in order to avoid the issue of collinearity in the analysis. The corresponding strata factor will not be included in the model.

Summary statistics (including number, mean, median, Q1, Q3, standard deviation, standard error, minimum and maximum) of BMD (lumbar spine, total hip, femoral neck) (baseline value, observed post-Baseline values, observed changes from Baseline and observed percent change from Baseline) will be provided at Week 26, Week 52 and Week 104 by treatment group. Graphical presentations will be used to examine trends over time using mean (\pm SE), mean change

from Baseline (\pm SE), and mean percent change from Baseline (\pm SE), at each of the scheduled visits (using OC).

The number (%) of patients with a percent change from Baseline in BMD $\geq 3\%$ at Week 104 will be also summarized. The number (%) of patients will be summarized by visit for each T-score category: normal (T-score ≥ -1.0); low bone density (T-score > -2.5 and < -1); osteoporosis (T-score ≤ -2.5).

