#### **4.5 RATIONALE FOR THE STUDY DESIGN AND CONTROL GROUP**

A parallel-group, randomized, controlled design was selected because trial participants are exposed to a single treatment and assignment to that treatment is based solely on chance. This design is free of the limitations of competing designs such as crossover in which there may be a carryover effect from one treatment to the following treatment, which can confound interpretation of efficacy and safety, especially in regards to some longer term effects, such as bone mass.

Randomization will be stratified by HbA1c at Screening ( $\leq 8.5\%$ ,  $>8.5\%$ ) and sex (male, female) to enable a balanced treatment assignment considering factors that can impact the primary and key secondary safety study endpoint. A placebo control will be used to allow for an unbiased assessment of treatment effects and safety data. Bias will be minimized by randomizing the patients to treatment groups, blinding the patients, the Investigators, and the Sponsor to the treatment allocations, and by adjudicating endpoints in a blinded fashion. A 2-week Run-in Phase has been implemented to stabilize HbA1c and minimize response to placebo and effects inherent to participation in a controlled clinical trial.

Sotagliflozin treatment for 26 weeks is considered to be of sufficient duration to observe effects on reduction of HbA1c, blood pressure (BP), and BW, and is, therefore, selected as the time point for assessment of the primary endpoint HbA1c. The double-blind controlled extension up to 104 weeks will provide additional long-term data on efficacy and safety, including long-term assessment of bone safety with sotagliflozin treatment.

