## 11 STATISTICAL CONSIDERATIONS

### 11.1 DETERMINATION OF SAMPLE SIZE

The sample size/power calculations were performed based on the primary variable of change from Baseline to Week 26 in HbA1c (%).

Assuming a common standard deviation (SD) of 1.2% and using a 2-sided test at a 0.05  $\alpha$ -level, 360 patients (120 patients per arm) will have 97% power to detect a treatment difference of -0.6% in mean HbA1c change from Baseline to Week 26 between sotagliflozin 400 mg and placebo.

This sample size will also allow to exclude a decline in BMD from Baseline of >2% with a 95% power, assuming a missing rate of 30% and an SD of 3.5%.

The total sample size will be approximately 360 patients to be randomized (120 in sotagliflozin 200 mg group, 120 in sotagliflozin 400 group, and 120 in placebo group).

Calculations were made using East 6.4 software.

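### The pattern-based BMD imputation has no treatment-by-sex structure, so where it is used the descriptive sex difference at Week 26 shrinks by about the missing fraction

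*SAP*

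**What the plan says.** SAP 2.4.5.1 gives two imputation methods for BMD.

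- **First choice, retrieved dropouts.** The model is built separately in each treatment group and names the randomization strata and baseline. It needs at least 5 retrieved dropouts in each group.
- **Pattern-based method.** Step 1 fills missing baseline BMD and includes the strata. Step 2 (MCMC) uses treatment and the BMD values. Step 3 reads: "The imputation model will include treatment, measurements at Baseline, Week 26, Week 52, and Week 104 in the VAR statement". For Week 26: "The imputation model at Week 26 for the topline analysis will include treatment and measurement at Baseline". This method is labelled a sensitivity analysis, but it takes over as primary at any timepoint where retrieved dropouts are insufficient.

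The same section plans BMD effects by age, diabetes duration, sex, BMI and eGFR at Weeks 26, 52 and 104. They come from an ANCOVA with a treatment-by-subgroup term and are shown in a forest plot, "using the same MI method as applied to each of the key safety endpoints, respectively".

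Protocol 4.5 says the trial is stratified by HbA1c and sex "to enable a balanced treatment assignment considering factors that can impact the primary and key secondary safety study endpoint".

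SAP Appendix C differs. It names LOCF as the alternative at Week 26 and MMRM at Weeks 52 and 104, and it lists no BMD subgroup analysis at the two later visits.

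**The concern.** The subgroup model estimates something that the imputation model rules out. With treatment as a single term and no sex, a missing woman and a missing man in the same arm with the same BMD history are imputed from the same equation. The imputed patients therefore carry the pooled treatment effect, and the estimated sex difference moves toward zero.

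Protocol 4.4 and 9.4 give a reason to look at women: weight loss can lower estradiol, which can affect bone. If harm were concentrated in women, the planned display would understate it there and attribute part of it to men.

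**Working it through.** **1. The plan's own figure.** Protocol 11.1 makes this claim: "This sample size will also allow to exclude a decline in BMD from Baseline of >2% with a 95% power". Its inputs for that claim are 30% missing data and an SD of 3.5 percentage points, and each of the three arms has 120 patients. I take the two-sided 0.05 level stated there for HbA1c, because none is given for BMD.
- Observed per arm: 120 × 0.7 = 84.
- SE of the difference: 3.5 × √(2/84) = 0.54.
- Power: Φ(2/0.54 − 1.96) = Φ(1.74) = 95.9%, against 95% stated. The inputs are reproduced.

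**2. Week 26 algebra.** Let m be the missing fraction (equal by arm and sex), w the share of women, and dW and dM the true effects. The pooled effect is d = w·dW + (1 − w)·dM.
- Women: (1 − m)·dW + m·d
- Men: (1 − m)·dM + m·d
- Sex difference: (1 − m)·(dW − dM)
- All patients: w × women + (1 − w) × men = d, unchanged.

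The documents give no effect by sex, so I assume dW = −2.0, dM = 0 and w = 0.5. At m = 0.3:
- Women: 0.7 × (−2.0) + 0.3 × (−1.0) = −1.7
- Men: 0 + 0.3 × (−1.0) = −0.3
- Difference: −1.4 instead of −2.0
- All patients: −1.0

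**3. Simulation.** 120 per arm, SD 3.5, missing completely at random, regression-mean imputation, 1,500 replicates. Each pair is for an assumed baseline sex gap in BMD of 0 and 0.10.

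| Missing | Algebra | Model as written |
|---|---|---|
| 10% | −1.8 | −1.80 / −1.78 |
| 20% | −1.6 | −1.59 / −1.62 |
| 30% | −1.4 | −1.44 / −1.42 |

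The all-patient effect at 30% missing was −0.99 to −1.00 (true −1.0).

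**4. What cures it (30% missing).** Adding sex as a main effect gives −1.39 / −1.42, no improvement: it shifts women equally in every arm and leaves the between-arm difference pooled. Sex with treatment-by-sex, which is equivalent to imputing by arm with sex, gives −2.00 / −2.05.

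**5. Intervals.** Proper MI with Rubin's rules (600 replicates, 30 imputations, 30% missing) gives a sex difference of −1.41 as written. Mean SE is 1.08, empirical SD 0.80, and 95% interval coverage about 97%.

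**6. Later visits.** In a two-visit model of Week 104 with 30% missing, the loss is 17% to 25% if Week 26 was observed in all those patients (between-visit correlation 0.9 down to 0.3). It is 28-30% if Week 26 was not observed. An earlier scan carries part of the sex signal.

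**7. Unequal missingness and the all-patient contrast.** Assume no drug effect, women losing 1.5% more in every arm, half women, and 40% of drug-arm women missing against 20% elsewhere. Ignoring baseline:
- Drug arm, observed: women 0.5 × 0.6 = 0.30 and men 0.5 × 0.8 = 0.40. Their mean, −1.5 × 0.30/0.70 = −0.64, is also the mean of the imputed values, so the arm mean is −0.64.
- Placebo mean: −0.75.
- Shift: about +0.11 points, or 0.11/0.54 = 0.2 SE. With sex in the imputation model it is close to zero.

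**The case against.** The strongest reply is that little hangs on this.

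- **Descriptive and imprecise.** No significance tests are planned for BMD, and the subgroup results are descriptive. With about 42 observed patients per sex per arm (84/2), the SE is 3.5 × √(2/42) = 0.76 for one sex and 0.76 × √2 = 1.08 for the difference. The 0.6-point loss above is about 0.56 SE.
- **Total error is no worse.** The shrunken estimate is also less variable. From the proper-MI run, root mean squared error is √(0.585² + 0.796²) = 0.99 as written. By arm it is about 1.01, nearly all of it variance.
- **Several conditions must hold.** The fallback must be triggered, the effect must differ by sex, and missingness must be high. The 30% is a sample-size assumption with no visit attached, and Protocol 6.2.2 asks sites to make every effort to obtain BMD after discontinuation.
- **The first-choice model is not a clean contrast.** It may drop a stratum for non-convergence, and the text then describes a simple regression on baseline.

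All of this stands and lowers the severity. It does not remove the bias. The shrinkage has a known direction, toward hiding a sex difference in a safety endpoint. It is not disclosed as shrinkage, and the forest plot, where it would appear, is the product of this analysis.

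**Conclusion.** The point holds, at minor to moderate severity. Where the pattern-based imputation is used and the treatment effect differs by sex, the Week 26 sex difference is understated by about the missing fraction. At Weeks 52 and 104 the loss is somewhat smaller where earlier scans exist. The sizes assume half the patients are women, missingness unrelated to outcome and equal across arms, and an illustrative effect of −2.0 in women and 0 in men. The proportion lost at Week 26 does not depend on that effect size. The other BMD subgroup factors are also absent from these models and would be attenuated in the same way.

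A reader might infer four stronger things that the documents and figures do not support:

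- **That the main BMD comparison is biased.** It is not under equal missingness. The shift of about +0.1 points needs an assumed sex-by-arm difference in missingness.
- **That leaving out the strata as covariates is the cause.** Sex as a main effect changes nothing, and the HbA1c stratum plays no part in the sex result. Its omission is a separate mismatch with the ANCOVA.
- **That the intervals are invalid.** Coverage was about 97%.
- **That this model is bound to be primary.** Section 2.4.5.1 makes that conditional, and Appendix C names other fallbacks.

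**What to change.** In SAP 2.4.5.1:

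1. Run steps 2 and 3 and the Week 26 topline model separately within each treatment group, with sex and HbA1c stratum in the variable list. Imputing by group is what restores the sex difference.
2. For the age, diabetes duration, BMI and eGFR subgroups, add the relevant factor to the within-group model.
3. Reconcile Appendix C with 2.4.5.1: state one fallback at Week 26 and one at Weeks 52 and 104, and say whether BMD subgroups are analyzed at the later visits.

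The cost is a few lines of SAP text and a small code change. Sex and HbA1c stratum are recorded for every randomized patient. The price is a more variable subgroup estimate: the empirical SD of the sex difference rises from 0.80 to 1.01 at 30% missing, in exchange for removing the bias.

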2.4.5.2 Analyses of hypoglycemia

Analyses of hypoglycemia will be performed on the TEAE period as defined in [Section 2.1.4](#). Hypoglycemia will be classified as severe hypoglycemia, documented symptomatic hypoglycemia, asymptomatic hypoglycemia, probable symptomatic hypoglycemia or relative hypoglycemia (See [Section 2.1.4.1](#)).

The number (%) of patients with 1) any hypoglycemia, 2) severe hypoglycemia and documented symptomatic hypoglycemia will be summarized respectively by treatment group during the TEAE period, as well as the incidence rate in patient years. Two types of incidence rates will be presented: the number of patients with event(s) per 100 patient-years (calculated as the number of patients with at least 1 event/ total exposure in 100 patient-years) and the total number of events per 100 patient-years (calculated as the total number of events / total exposure in 100 patient-years). Note: Note: here exposure in days is duration of treatment-emergent AE period, ie, duration of IMP treatment in days +1 ([Section 2.1.4](#)).

The summary of frequency and incidence rate in patient-years for severe hypoglycemia or documented symptomatic hypoglycemia will be provided as appropriate by gender, age group (≥ 55 to < 65 , ≥ 65 years), race (White, Black or African American, Asian, Other).

A KM curve will be provided by treatment group for the time to first severe hypoglycemia or documented symptomatic hypoglycemia during the TEAE period for the 104-week entire treatment period only (see [Section 2.4.5](#)).

Documented symptomatic hypoglycemia may be presented by ≤ 70 mg/dL (3.9 mmol/L) and < 54 mg/dL (3.0 mmol/L) respectively, as appropriate.

A listing of patients for all events reported on the dedicated e-CRF “Hypoglycemic event information” page will be provided with each category flagged (ie, severe hypoglycemia, documented symptomatic hypoglycemia, asymptomatic hypoglycemia, probable symptomatic hypoglycemia and relative hypoglycemia).

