### **Observation period of safety endpoints**

The observation period of safety data will be divided into 3 segments:

- The pretreatment period is defined as the time between the date of the informed consent and the first dose of double-blind IMP.
- The treatment-emergent period (TEAE period) is defined as the time from the first dose of double-blind IMP up to 10 days (1 day for hypoglycemia) after the last dose of double-blind IMP, regardless of the introduction of rescue therapy. The 10-day interval is chosen based on the half-life of the IMP (approximately 5 times the half-life of sotagliflozin in patients with moderate renal dysfunction).
- The post-treatment period is defined as the time starting 11 days after the last dose of double-blind IMP (after the treatment-emergent period).

The Baseline value for safety endpoints in the safety population is the last available value prior to the first administration of the double-blind IMP.

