The treatment-emergent adverse event (TEAE) period will include both **treatment** and **residual treatment** epochs. (See the TEAE period for the 26-week core treatment period in [Section 2.5.4](#)).

- The **posttreatment** epoch is defined as the period of time starting the day after the end of the treatment-emergent adverse event period up to the last protocol-planned visit or the resolution/stabilization of all serious adverse events (SAE), adverse events of special interest (AESI) and events of special interest (EOSI), whichever is later.

The **on-study observation period** is defined as the time from start of double-blind treatment until the end of the study (defined as the last scheduled visit for those who completed the study and the date collected on e-CRF page “Completion of End of Study/Follow-up” for those who did not complete the study).

The **post-study observation period** is defined as the time from the day after the end of the study until the resolution/stabilization of all SAE, AESI and EOSI if applicable.

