(male, female), subgroup factor, treatment-by-subgroup factor, and country as fixed factors and using baseline HbA1c value as a covariate. The adjusted estimates of treatment mean differences (sotagliflozin 400 mg versus placebo and sotagliflozin 200 mg versus placebo) with SE and 95% CIs will be provided as appropriate across the subgroups. A forest plot of the results will also be presented.

In the case that the subgroup factor is identical or similar to a randomization strata factor (eg, baseline HbA1c category or sex), only the subgroup factor (as a single factor and/or an interaction term) will be included in the model in order to avoid the issue of collinearity in the analysis. The corresponding strata factor will not be included in the model.

Summary statistics at scheduled visits

Summary statistics (for screening value, baseline value, observed post-Baseline value and its changes from Baseline) at scheduled visits will be provided for each treatment group. The summary will include the number of observations, mean, SD, SE, minimum, median, and maximum. Graphical presentations will also be used to examine trends over time using mean values (\pm SE) and mean changes from Baseline (\pm SE) at each of the scheduled visits.

Similar presentations will be provided excluding measurements after rescue therapy during the entire 104-week double-blind treatment period.

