- All treatment-emergent adverse event by primary SOC, HLGT, HLT, and PT, showing number (%) of patients with at least 1 treatment-emergent adverse event sorted by the SOC internationally agreed order. The other levels (HLGT, HLT, PT) will be presented in alphabetical order.
- Number (%) of patients experiencing TEAE(s) presented by PT, sorted by decreasing incidence of PT in the sotagliflozin 400 mg group.
- All treatment-emergent adverse events by primary SOC and PT, showing the number (%) of patients with at least 1 treatment-emergent adverse event, sorted by the internationally

agreed SOC order and by decreasing incidence of PTs within each SOC in the sotagliflozin 400 mg group. This sorting order will be applied to all similar other tables, unless otherwise specified.

- All treatment-emergent adverse events regardless of relationship and related to IMP by primary SOC, HLGT, HLT and PT, showing the number (%) of patients with at least 1 treatment-emergent adverse event, sorted by the internationally agreed SOC order. The other levels (HLGT, HLT, PT) will be presented in alphabetical order.
- All treatment-emergent adverse events by maximal severity, presented by primary SOC and PT, showing the number (%) of patients with at least 1 treatment-emergent adverse event by severity (ie, mild, moderate, or severe), sorted by the sorting order defined above.
- Common TEAEs (PTs with incidence $\geq 2\%$ in any treatment group) by primary SOC, HLGT, HLT and PT, sorted by the internationally agreed SOC order. The other levels (HLGT, HLT, PT) will be presented in alphabetical order.
- Common TEAEs (PTs with incidence $\geq 2\%$ in any treatment group) will be provided as appropriate by primary SOC and PT and by demographic factors including gender, age group (≥ 55 to < 65 , ≥ 65 years), race (White, Black or African American, Asian, other), baseline SBP category (< 130 , ≥ 130 mmHg), and baseline eGFR category (≥ 30 to < 60 mL/min/1.73m² [Moderate decrease in GFR], ≥ 60 to < 90 mL/min/1.73m² [Mild decrease in GFR], and ≥ 90 mL/min/1.73m² [Normal]), prior antidiabetic medication [Insulin (alone or with other antihyperglycemic agents), SU and/or glinide (alone or with other non-insulin antihyperglycemic agents), Other (non-insulin antihyperglycemic agents except SU, and glinide)]. SOC will be sorted by the internationally agreed order and the PT by decreasing incidence within each SOC in the sotagliflozin 400 mg group, as described above.

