
For time to event analysis/KM plot, time to event (eg, treatment discontinuation, rescue therapy, hypoglycemia, etc) is defined as the number of days from the date of the first administration of double-blind IMP (or the date of randomization if not exposed) to the start date of the first occurrence of the event during the respective analysis period.

Patients who did not experience any event during the respective analysis period are considered censored observations. The censoring rules are defined below:

Time to event	Censoring date at Week 26 (1st step analysis)	Censoring date at EOT/EOS (2nd step analysis)
Treatment discontinuation due to any reason	Not applicable	EOT
Treatment discontinuation due to AE	Not applicable	EOT
Time to rescue	min (EOT, Date of W26 visit)	EOT
Time to severe or documented hypoglycemia	min (EOT+1, EOS, Date of W26 visit). See Section 3	Min (EOT+1, EOS)

Note: (1) Day 182 will be used if Date of Week 26 visit (or date of W26/re-allocated W26) is not available.

(2) Date of EOS will be used if date of EOT is not available; Last contact date will be used if date of EOS is not available.

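### Hypoglycemia is summarized only over all time on study drug, with no pre-rescue comparison and no split by insulin or sulfonylurea background; adding both is a cheap improvement

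*SAP*

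**What the plan says.** **Analysis period.** SAP 2.4.5.2: "Analyses of hypoglycemia will be performed on the TEAE period as defined in" SAP 2.1.4, where the TEAE period "will include both treatment and residual treatment epochs". Both epochs are set by study-drug dates alone, with a one-day tail for hypoglycemia. SAP 2.1.4 does not mention rescue. The explicit rule is in the protocol (9.2, Observation period of safety endpoints), which extends the period to 10 days (1 day for hypoglycemia) "after the last dose of double-blind IMP, regardless of the introduction of rescue therapy".

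**Denominator and censoring.** For the rates, "here exposure in days is duration of treatment-emergent AE period, ie, duration of IMP treatment in days +1". In SAP 2.5.4, first-step censoring for time to severe or documented hypoglycemia is "min (EOT+1, EOS, Date of W26 visit"), and second-step censoring is the earlier of EOT+1 and EOS. SAP section 3 uses the common cut-off date at the first step. None of these stops at rescue.

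**Rescue.** SAP 2.1.2.1 allows oral drugs or insulin, excluding only SGLT2 inhibitors and thiazolidinediones. Under Protocol 8.2.2 blinded study drug continues after rescue.

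**Subgroups.** SAP 2.4.5.2 gives summaries "for severe hypoglycemia or documented symptomatic hypoglycemia will be provided as appropriate by gender, age group" and race; Appendix C lists the same three factors.

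**Contrast within the SAP.** For HbA1c by visit, SAP 2.4.4.1 adds: "Similar presentations will be provided excluding measurements after rescue therapy during the entire 104-week double-blind treatment period". The same section uses prior antidiabetic medication as an HbA1c subgroup. SAP 2.4.5.3 splits common TEAEs by "prior antidiabetic medication [Insulin (alone or with other antihyperglycemic agents"), and by further categories.

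**The concern.** Two separate gaps bear on what the trial can say about hypoglycemia caused by sotagliflozin.

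The first is rescue. Protocol 4.6 names insufficient glucose control as a risk mainly in the placebo arm, and the thresholds in Protocol 8.2.2 tighten over time. If sotagliflozin lowers HbA1c, more placebo patients should receive open-label rescue, some of it insulin. Hypoglycemia following rescue is credited to the randomized arm. That raises the placebo count more than the sotagliflozin count and shrinks any excess on sotagliflozin. A finding of no imbalance would then be hard to interpret: it could reflect the drug, or rescue on placebo.

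The second is background therapy. Patients may enter on diet alone, oral drugs, insulin or GLP-1 agonists, and randomization is stratified only by screening HbA1c and sex. If an excess arises mainly in insulin or sulfonylurea users, an overall figure dilutes it. The TEAE split does not fill this gap: hypoglycemia is identified from its own e-CRF page (SAP 2.1.4.1) and is also reported as an SAE only when it meets the criteria for one.

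**Working it through.** **The plan's own figures.** The documents give no rate, precision or power figure for hypoglycemia or rescue. The stated design figures concern other endpoints and reproduce: HbA1c (120 per arm, difference 0.6, SD 1.2, two-sided 0.05) gives 97.2% against the stated 97%; BMD (120 × 0.7 = 84 per arm, 2%, SD 3.5%) gives 95.9% against the stated 95%.

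**Rescue: inputs, all assumed.**
- RR = 1.5, the true pre-rescue sotagliflozin/placebo rate ratio.
- fp and fs, the shares of person-time after rescue on placebo and sotagliflozin.
- k, the factor by which rescue raises the event rate.

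The protocol supports fp > fs in direction only.

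**Formulas**, in units of the pre-rescue placebo rate:
- Placebo: (1 − fp) + fp·k = 1 + fp(k − 1)
- Sotagliflozin, drug effect persists after rescue: RR × [1 + fs(k − 1)]
- Sotagliflozin, drug effect vanishes after rescue: (1 − fs)·RR + fs·k

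The reported ratio is sotagliflozin divided by placebo. With 25%/10% and k = 3, placebo is 0.75 + 0.25 × 3 = 1.50. Sotagliflozin is 1.5 × 1.20 = 1.80 if the effect persists (ratio 1.20), or 0.90 × 1.5 + 0.10 × 3 = 1.65 if it vanishes (ratio 1.10).

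| fp / fs | k | Effect persists | Effect vanishes |
|---|---|---|---|
| 15% / 7% | 2 | 1.40 | 1.33 |
| 15% / 7% | 3 | 1.32 | 1.23 |
| 15% / 7% | 4 | 1.25 | 1.16 |
| 25% / 10% | 2 | 1.32 | 1.24 |
| 25% / 10% | 3 | 1.20 | 1.10 |
| 25% / 10% | 4 | 1.11 | 1.00 |
| 40% / 20% | 2 | 1.29 | 1.14 |
| 40% / 20% | 3 | 1.17 | 1.00 |
| 40% / 20% | 4 | 1.09 | 0.91 |

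The last row is 1.5 × 1.6 / 2.2 = 1.09, or (0.80 × 1.5 + 0.20 × 4) / 2.2 = 0.91.

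**Sensitivity.** With a persisting effect, the ratio reaches 1 at k = 1 + (RR − 1)/(fp − RR·fs). That is 6.0 for 25%/10% and also for 40%/20%, both outside the grid. With a wider imbalance of 40%/15% it is 1 + 0.5/0.175 = 3.86, so a persisting effect could be masked there. With equal shares and a persisting effect there is no distortion.

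**Background dilution: inputs assumed.** Among insulin or sulfonylurea users, 20% on placebo and 35% on sotagliflozin have an event (15 points, ratio 1.75). Among all others, 2% in each arm do. For a user share w, the arm percentage is w × (user percentage) + (1 − w) × 2%.

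| w | Placebo | Sotagliflozin | Difference | Ratio |
|---|---|---|---|---|
| 20% | 5.6% | 8.6% | 3 points | 1.54 |
| 40% | 9.2% | 15.2% | 6 points | 1.65 |
| 60% | 12.8% | 21.8% | 9 points | 1.70 |

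The absolute difference is diluted much more than the ratio.

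**The case against.** A reader might go further than the documents allow in three ways.

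**That this is the only hypoglycemia comparison.** It is not. SAP 2.4.5 summarizes safety for the 26-week core period separately, when rescue thresholds are looser. Appendix C plans frequency by weekly interval, and Protocol 11.4.3.3 promises an assessment of the pattern over time. SAP 2.4.4.3 gives rescue counts and time-to-rescue curves by arm. An early excess or a rescue imbalance could be seen. This stands. Even so, the 26-week table also counts post-rescue events, and no listed output relates hypoglycemia to rescue by arm.

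**That the analysis is biased.** Counting all events on study drug matches the de facto approach used for efficacy and is valid for the question it answers. Attenuation arises only when the result is read as drug-attributable, and it needs both more post-rescue time on placebo and a higher rate after rescue. The documents quantify neither. Rescue need not be insulin or a sulfonylurea. The threshold after Week 52 (HbA1c of at least 7.5%, without the exemption for a fall of at least 1.0%) could also bring many sotagliflozin patients into rescue.

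**That chance imbalance in background therapy cannot be separated from a drug effect.** Prior antidiabetic medication is tabulated by arm (SAP 2.1.1 and 2.4.1), so imbalance would be visible, and randomization balances it on average. What remains is the missing split of the outcome itself.

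Cutting at rescue is also not a clean contrast: it removes follow-up from the most hyperglycemic patients, and differently by arm. Safety analysis here is descriptive, so no formal conclusion turns on these tables.

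**Conclusion.** This is a cheap improvement to a valid plan, not an error in it. The planned count can attenuate a sotagliflozin excess when read as drug-attributable. On the assumed grid, a true ratio of 1.5 appears as about 1.40 to 1.09 if the effect persists after rescue, which is plausible because study drug continues. The 0.91 figure requires the effect to vanish. The direction follows from the protocol's own expectation for the placebo arm. The size is unknown, since every rate, share and multiplier above is assumed. The model also takes rates as constant within the pre- and post-rescue periods. The background gap is a separate matter of dilution, and a background split would do nothing about rescue.

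**What to change.** In SAP 2.4.5.2 and Appendix C, keep all existing hypoglycemia tables and add, for severe and documented symptomatic hypoglycemia:

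1. A supplementary by-arm count, rate and Kaplan-Meier curve with events and exposure cut at the first rescue medication. Use the same e-CRF rescue flag and start date as the planned time-to-rescue curve. Show it beside the all-events table, with a label saying that the cut is selective.
2. Prior antidiabetic medication in the hypoglycemia subgroup list, using the four-category version in SAP 2.1.1 (none; insulin; sulfonylurea and/or glinide; other).

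The cost is SAP wording and a few extra tables. Rescue dates, background categories and hypoglycemia records are already collected. The downsides are the selection introduced by the cut and small numbers in some background categories. Both additions should stay descriptive and be specified before unblinding.
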